## **7.9 Treatment Compliance**

### **Drug Accountability**

The Investigator is accountable for all clinical drug supplies shipped to his/her study site for the duration of the study. A final accounting of the clinical drug supplies will be required at the completion/termination of the study. The Investigator is required to provide written explanation for any discrepancies.

[figure not shown]
All used and unused clinical drug supplies will be inventoried and returned to the Sponsor (or an authorized representative) by a designated monitor.

The Investigator will not be permitted to return or destroy used or unused clinical drug supplies or packaging materials unless authorized by the Sponsor (or authorized representative).

## 8 STUDY ASSESSMENTS AND FLOW CHART

[figure not shown]
### 8.1 Efficacy Measurements

- **Symptoms of dyspepsia using Leeds Dyspepsia Questionnaire (LDQ)**
- LDQ Questionnaire will be completed by the site staff through interview with patient by site staff trained on administration of LDQ to capture the overall symptomatology at screening (visit 1), week 4 (visit 3) and on week 8 (visit 4). The symptoms of dyspepsia are evaluated by measuring its frequency using the LDQ questionnaire which is a fully validated instrument to assess the symptoms of dyspepsia. A dyspepsia questionnaire or Leeds Dyspepsia Questionnaire (LDQ) can identify subjects with dyspepsia by measuring its frequency and therefore will assess the severity via a calculated overall score

### **Quality of Life assessment using Short Form - Nepean Dyspepsia Index (SF-NDI)**

- Quality of life is an important health outcome, which is frequently measured in various clinical and epidemiological studies. Disease can have various effects on quality of life, it depends on the area of the body afflicted and how significant that area is to the individual.
- So, evaluating items by the individual patient according to their relative importance may be helpful and beneficial. This could be a more accurate method for evaluating how a disease affects the quality of life.
- The Short Form Nepean Dyspepsia Index (SF-NDI) was designed to evaluate the impairment in each component of a subject's life as wander ability to participate and enjoy these aspects of their lives.
- Short Form Nepean Dyspepsia Index (SF-NDI) Questionnaire will be used to measure the disease-specific Quality of Life of each participant of both arms (Test and Control Arm) at baseline (visit 2) and week 8 (visit 4).

[figure not shown]
### **Symptoms of dyspepsia assessed by Numerical Rating Scale (NRS 11)**

- The Numerical Rating Scale is widely used for self-reporting of pain intensity in clinical practices. In this study, the participants will be provided with the NRS 11 scale to mark changes for symptoms of sensation of bloating, early satiety, postprandial fullness, upper abdominal pain or discomfort (epigastric pain, epigastric burning), anorexia (loss of appetite), heartburn, nausea and vomiting at baseline and after 4 and 8 weeks of treatment.
- NRS 11 will be used to assess responders' analysis for adequate/satisfactory relief.
- NRS 11 and drug intake will be captured in patient diary. Drug intake will be recorded by the subject on a daily basis, symptoms will be recorded by the subject over the last two weeks prior to the visits. In addition, the baseline NRS 11 scores will be captured on site.

SYMPTOMS	SCALE										
	0	1	2	3	4	5	6	7	8	9	10
	No	Very Mild	Discomforting	Tolerable	Distressing	Very Distressing	Intense	Very Intense	Horrible	Unbearable	Unpeakable
Bloating sensation											
Early satiety											
Postprandial fullness											
Upper abdominal pain or discomfort (epigastric pain, epigastric burning)											
Anorexia (loss of appetite)											
Heartburn											
Nausea											
Vomiting											

**Treatment acceptance and ease of use assessed by Likert Scale**

- A 5-point Likert scale is a unidimensional scale which is used to collect responders' opinions and acceptance for the provided medications.
- The treatment acceptance and ease of use will be assessed by subjects by answering the question "Are you satisfied with the schedule of dosing of your treatment?" using the 5-point Likert scale.
- 5-point Likert scale includes scale consisting of five points on which responders have to record their opinion to the question mentioned above.
- These five points include 1. Not at all satisfied, 2. Slightly satisfied, 3. Neutral, 4. Very satisfied, 5. Extremely satisfied.

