#### 4.2 Discussion of Study Design, Including the Choice of Control Groups

This is an open label, randomized, multicenter, parallel-group, active-controlled Phase 3 study to evaluate the non-inferiority/ comparative efficacy of Itopride Hydrochloride 150 mg extended release tablets (administered once daily) compared to Itopride Hydrochloride 50 mg film coated tablets (administered TID) in subjects with functional dyspepsia.

The study will screen approximately 700 subjects and include 564 subjects (282 subjects in both arms Test and Active control arm) and the treatment will be given as follows.

- Test group - Itopride Hydrochloride 150 mg extended release tablets once daily before any of the main meals (preferably same meal throughout the treatment)
- Active Control group - Itopride Hydrochloride 50 mg film coated tablets 3 times daily before meals

The duration of treatment will be 8 weeks and the subject follow up will be one week after the end of treatment.

In the company-sponsored studies for the efficacy and effectiveness in FD, the total planned treatment duration was 2 to 8 weeks.

The study design is chosen as non-inferiority study with statistical considerations for sample size and non-inferiority margin as described in the statistical section 10.7.

An open-label design was chosen because one tablet of Itopride Hydrochloride 150 mg extended release tablets will be compared with three tablets of Itopride Hydrochloride 50 mg film coated tablets which allows to investigate the benefit of a lower tablet intake and the preference for the treatment. Itopride hydrochloride is used for the treatment of functional dyspepsia (FD) and is currently being dosed 50 mg thrice daily. Itopride Hydrochloride 150 mg extended release once daily tablets are a strategic life cycle management opportunity. By reducing the dose to once daily instead of thrice daily, the product may improve patient compliance and adherence. This may have, in particular in subjects with FD, a beneficial effect on the outcome of the related symptomatology and disease progression.

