## Exploratory analysis

### ▪ Treatment acceptance and ease of use assessed by using 5-point Likert Scale

The subject's response of treatment acceptance for each point i.e. 1-Not at all satisfied, 2-Slightly satisfied, 3-Neutral, 4-Very satisfied, 5-Extremely satisfied will be summarized descriptively, using frequency count (n) and percentages (%) by Test group and Active Control group at the end of the study treatment (i.e., at week 8).

A descriptive summary of treatment acceptance will also be provided using number of non-missing observation (n), median, minimum (Min) and maximum (Max) by Test group and Active Control.

To find the significant difference of acceptance and ease of use between Test group and Active Control group a two-sample t-test or Mann Whitney test will be used at 5% level of significance based the normality of the data.

Normality of the response of 5-point likert scale scores will be checked by using Q-Q Plot or KS test.

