**By NRS-11 Score:**

The subject is considered to be as responder if, each NRS11 symptoms change from baseline score at the end of the study treatment is at least 2 (i.e., NRS-11 symptoms CFB  $\geq -2$ ). only subjects with a score of the respective symptom of at least 5 at baseline will be used.

▪ **Treatment acceptance and ease of use assessed by Likert Scale**

Convert the responses of treatment acceptance into numeric score as follows and analyze the scores:

Acceptance response	Score
Not at all satisfied	1
Slightly satisfied	2
Neutral	3
Very satisfied	4
Extremely satisfied	5

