**Table 10.1.2.3.1.1: Treatment Acceptance & Ease of Use Assessment**

FULL ANALYSIS SUBJECT SAMPLE

Response	Statistics	
 (N=xxx)	
 (N=xxx)
Missing	n (%)	xx.x (x.x)	xx.x (x.x)
1-Not all satisfied	n (%)	xx.x (x.x)	xx.x (x.x)
2-Slightly satisfied	n (%)	xx.x (x.x)	xx.x (x.x)
3-Neutral	n (%)	xx.x (x.x)	xx.x (x.x)
4-Very satisfied	n (%)	xx.x (x.x)	xx.x (x.x)
5-Extremely Satisfied	n (%)	xx.x (x.x)	xx.x (x.x)
Treatment Acceptance	n	xxx	xxx
	Mean (SD)	xx.x (x.x)	xx.x (x.x)
	Median	xx.x	xx.x
	Min/Max	xx/xx	xx/xx
p-value		x.xxx	

Note 1: Percentages are based on the number of subjects allocated to treatment.

Note 2: P-value is calculated by using two sample t-test or Mann Whitney U test..

Source: LXX00X.sas, <CRO>.Run DDMMYYYY HH:MM  
Abbott Protocol CCCC-xxx-yyyy

Page x/y

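### The treatment-acceptance item codes 'Slightly satisfied' below 'Neutral', so its 1–5 score and the p-values built on it have no clear direction between those two answers

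*Protocol*

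**What the plan says.** Protocol 8.1 asks one question about acceptance, "Are you satisfied with the schedule of dosing of your treatment", and describes the instrument in these terms: "A 5-point Likert scale is a unidimensional scale which is used to collect responders' opinions and acceptance for the provided medications". The options are then listed: "These five points include 1. Not at all satisfied, 2. Slightly satisfied, 3. Neutral, 4. Very satisfied, 5. Extremely satisfied".

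The SAP keeps the same labels in the same order under its exploratory analysis (following 4.2.2): "1-Not at all satisfied, 2-Slightly satisfied, 3-Neutral, 4-Very satisfied, 5-Extremely satisfied will be summarized descriptively". SAP 5.3.2 assigns the numbers: "Convert the responses of treatment acceptance into numeric score as follows and analyze the scores". For the arm comparison the SAP says that "a two-sample t-test or Mann Whitney test will be used at 5% level of significance based the normality of the data", with normality judged by Q-Q plot or KS test.

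The SAP text summarises the score by n, median, minimum and maximum. The shells for Tables 10.1.2.3.1.1 and 10.1.2.3.1.2 add a mean (SD) and print a p-value. The note to the overall table reads: "P-value is calculated by using two sample t-test or Mann Whitney U test". SAP 4.7 repeats the analysis by gender, age group and country.

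Acceptance is an exploratory objective in Protocol 3.3 and SAP 3.3. The protocol synopsis also lists it among the secondary endpoints.

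**The concern.** A t-test and a rank test on a 1–5 code both need a larger number to mean more of the thing measured. Here, a subject who reports some satisfaction scores 2 and a subject who reports none either way scores 3. 'Not at all satisfied' is the only negative option, so a mildly dissatisfied subject has no matching category.

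A mildly satisfied subject can follow the label and tick 2, or follow the position on the scale and tick 3 or 4. Once the answers are collected, the two kinds of subject cannot be told apart.

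The dosing schedule is what this item asks about and what differs between the arms. Protocol 4.2 defends the open-label design partly because it "allows to investigate the benefit of a lower tablet intake and the preference for the treatment", and this is the only direct measure of satisfaction with, or preference for, the schedule.

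**Working it through.** **Labels against codes.** Protocol 8.1, the SAP exploratory analysis, SAP 5.3.2 and both shells give the same order, apart from small wording slips in the shells. It is therefore not an error in one place. Neither document says that 'Neutral' stands for 'moderately satisfied'.

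| Code | Label | Type of label |
|---|---|---|
| 1 | Not at all satisfied | one-way intensity |
| 2 | Slightly satisfied | one-way intensity |
| 3 | Neutral | midpoint of a two-way scale |
| 4 | Very satisfied | one-way intensity |
| 5 | Extremely satisfied | one-way intensity |

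**Effect on the mean.** If a share *d* of one arm answers 'Slightly satisfied' instead of 'Neutral' and all else is equal, its mean changes by *d* × (2 − 3) = −*d*. With codes 2 and 3 exchanged, it changes by *d* × (3 − 2) = +*d*.

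**Illustration.** The documents give no distribution of answers, so these counts are assumed. Only the 282 per arm comes from Protocol 10.7. Control counts for codes 1 to 5 are 14, 28, 84, 99 and 57. The test arm is the same except that 14, 28 or 56 subjects answer 2 instead of 3.

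| Subjects differing | Mean difference, as coded | Mean difference, 2 and 3 exchanged | t-test p (as coded / exchanged) | Mann-Whitney p (either coding) |
|---|---|---|---|---|
| 14 | −14/282 = −0.05 | +0.05 | 0.59 / 0.63 | 0.67 |
| 28 | −28/282 = −0.10 | +0.10 | 0.29 / 0.33 | 0.40 |
| 56 | −56/282 = −0.20 | +0.20 | 0.042 / 0.042 | 0.093 |

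Written out for 56 subjects, as coded:
- Control: (14 + 56 + 252 + 396 + 285)/282 = 1003/282 = 3.56.
- Test: (14 + 168 + 84 + 396 + 285)/282 = 947/282 = 3.36.
- Exchanging codes 2 and 3 swaps these two means.

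**Median.** In this example it does not move. In both arms 126 of 282 subjects answer 1, 2 or 3, fewer than half, so the median is 4 under either coding. It is sensitive to the order of 2 and 3 only when it falls among those options.

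**Proportion answering 4 or 5.** This is (99 + 57)/282 = 55.3% in each arm, whatever the order of 2 and 3. The difference is 0, with 95% half-width 1.96 × √(2 × 0.553 × 0.447/282) = 0.082, or 8.2 percentage points.

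**How many tests rest on the score.** One overall, plus 2 for gender, 3 for age group and 5 for country: 1 + 2 + 3 + 5 = 11 p-values.

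**The case against.** The strongest defence is that the item matters little and that the raw answers stay visible. Acceptance is exploratory in both lists of objectives, and nothing in the non-inferiority decision depends on it. Table 10.1.2.3.1.1 is not marked for headline results in the SAP output list. The SAP also requires n (%) for every category by arm, so a reader can see how many subjects chose 2 and 3. All of this stands. It limits the problem to the summary score and its p-values.

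A reader might go further and infer that the score carries the wrong sign. The documents do not support that. Subjects who answer by position use the codes in the intended direction, and the scale graphic is not visible in the text available, so layout cues cannot be judged. Between options 2 and 3 the direction is ambiguous, and reversed only for those who answer by label.

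A reader might also infer that nothing else measures the benefit of fewer tablets. Protocol 4.2 describes that benefit largely as better compliance and adherence, which are measured separately by the daily diary, by drug accountability and by the compliance calculation in SAP 5.5.1.

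The example is extreme by construction, since all the movement lies between two options; a shift into 4 or 5 would be scored correctly. Its nominally significant result comes from the t-test alone. The SAP chooses the test by a normality check, which a five-level item with several hundred subjects would probably fail, and that would lead to the Mann-Whitney test (p = 0.093).

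**Conclusion.** The point holds as a defect in how the scale is built and scored. The documents agree with each other on it. The summary score, overall and in every subgroup, cannot be read as higher meaning more satisfied, because options 2 and 3 have no defensible order. The mean shifts by one hundredth of a point for each percentage point of subjects who differ between those two options, and the sign of the shift depends on how subjects read the scale. The ±0.20 figure rests on assumed counts and shows the mechanism; it does not forecast the result.

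The primary LDQ analysis, the sample size and the n (%) table are unaffected. The point is worth correcting because the SAP plans significance tests on this score and Protocol 4.2 gives preference a part in justifying the open-label design.

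**What to change.** **If the form is not yet in use:** relabel the item with one monotone set and keep the question. Either a balanced scale (Very dissatisfied, Dissatisfied, Neutral, Satisfied, Very satisfied) or a one-way scale with 'Moderately satisfied' at 3 would do. Change Protocol 8.1, the exploratory analysis following SAP 4.2.2, SAP 5.3.2 and the shells. The cost is one CRF item and its translations.

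**If the form is in use:** do not relabel, since that would mix two instruments. Before database lock, make the arm comparison the proportion answering 4 or 5, described as very or extremely satisfied, with the difference and its 95% CI. Report the five categories as counts, without a mean or a score test. Only the SAP text and shells change.

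The second route has a price. Dichotomising loses information and groups 'Slightly satisfied' with the lower categories; in the example above it shows no difference at all. Nor does it recover the meaning of answers given by position instead of label.

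In either case, align the summary statistics (the mean is in the shells but not in the SAP text). If any score test is kept, correct the note to the by-gender shell, which names a Wilcoxon signed rank test, a paired method, where the SAP text specifies Mann-Whitney.

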**5-point Likert Scale****8.2 Safety Measurements****Adverse Events**

Requirements for collecting, recording and reporting of AEs are described in Section 9. Each subject is to be evaluated at the termination visit. Should any AE be identified at this visit, the Investigator will continue to follow the subject as described in Section 9.1.2.

Safety Laboratory data will be collected for the determination of the following parameters:

**Laboratory evaluation:**

The following laboratory parameters will be evaluated:

1. Hematology – Hemoglobin, hematocrit, red blood cell (RBC) count, white blood cell (WBC) count, platelet count, and differential blood count (only if indicated)
2. Biochemistry -

Random blood sugar, liver function tests [ serum bilirubin, alkaline phosphatase, ALT (alanine amino transferase), AST (aspartate amino transferase), LDH (lactate dehydrogenase), gamma-glutamyl transferase], calcium, potassium, Serum Prolactin (Fasting), Serum Lipase (only baseline)

For all laboratory parameters with values outside the normal range (or abnormal results), the clinical significance will be judged by the Investigator.

### Vital Signs

Height will be recorded at screening only and weight will be recorded at all visits.

Body temperature, pulse rate, respiration rate, blood pressure, will be recorded at baseline and at every visit during the study period.

Systolic blood pressure (SBP), diastolic blood pressure (DBP) and pulse rate are to be measured while the subject is in sitting position after 5 minutes rest.

### 12-Lead Electrocardiogram (ECG)

A 12-lead ECG must be recorded while the subject is in supine position after 5 minutes rest at screening.

The ECG should be interpreted by the Investigator (normal/abnormal). For abnormal ECGs the clinical significance (yes/no) should be judged by the Investigator and the abnormality is to be specified. These subjects with clinically significant ECG abnormalities will not be included into the study.

### Physical Examination

A physical examination should be performed and any relevant findings are to be recorded on the Medical History form in the CRF (for findings from the past that occurred prior to screening visit), or on the Adverse Event form in the CRF for findings presently occurring. This will be done at visit 1, 2, 3 and 4.

### Pregnancy test

Urine pregnancy test (dipstick) will be done in all female subjects of child-bearing potential at the time of screening, to rule out pregnancy (if not postmenopausal or following tubal ligation or hysterectomy).

## **8.3 Other Assessments**

### Informed Consent

Voluntary written informed consent must be obtained from each subject (or their legally acceptable representative) prior to performing any study-related procedures (see Section 1.3).

#### Demographic Data

Demographic data (gender, age, race) will be collected for all subjects.

#### Medical History

Any clinical event, including diagnosis, condition, or surgery, that occurred prior to the screening visit (before the informed consent is signed), is to be recorded on the Medical History form in the eCRF. In case a clinical event concerns a chronic disorder, which means it started in the past and it is still present at the screening visit, it should also be recorded on the Medical History Form in the eCRF. Examples of these events are diabetes, migraine, and hay fever (documentation of pregnancy, see section 9.3).

#### Concomitant Medication

All medication taken by the subject during the study (from signing the informed consent form through post-study follow-up) is to be recorded on the Concomitant Medication form in the eCRF, except for study drug.

#### Compliance and treatment adherence

The information about drug intake/adherence and NRS 11 self-reporting of symptoms will be captured in Patient diary. Drug intake will be recorded by the subject on a daily basis, symptoms will be recorded by the subject over the last two weeks prior to the visits. In addition, the baseline NRS 11 scores will be captured on site.

### **8.4 Appropriateness of Measurements**

All measurements will be performed using standard methods which are generally recognized as being reliable, accurate, and relevant.

### **8.5 Primary Efficacy Variable(s)**

The change in the overall severity of functional dyspepsia between baseline and week 8, as measured by the Leeds Dyspepsia Questionnaire (LDQ) severity score has been selected as primary endpoint.

LDQ is a useful tool for assessing the presence and severity of dyspepsia. In a study by Moayyedi et al., the LDQ had a high degree of sensitivity in detecting dyspepsia compared to the opinion of a gastroenterologist or a General Physician as the gold standard. LDQ questionnaire is validated in primary and secondary care populations and hence is suitable for general practice dyspepsia studies.

Holtmann et al. investigated this parameter with Itopride in a placebo-controlled study. Other studies have used LDQ for FD as primary endpoint.

## 8.6 Flow Chart of Study Assessments

All study assessments will be conducted as indicated in Table 2, which displays the frequency and timing of all measurements.

**Table 2:** Study Assessments

Periods	Screening period	Treatment period			Follow up
Visits (V)	V1	V2	V3	V4 (ET/ED)	TC
Week			W4	W8	
Day	Day -1	Day 1	Day 29	Day 57	Day 64
Visit window	-14 to -1 days		±1 day	±1 day	+1 day
Informed Consent	X				
Demographic data	X				
Medical history	X				
Inclusion/Exclusion criteria	X	X			
Physical examination	X	X	X	X	
Weight, Height (screening only), BMI 	X	X	X	X	
Vital signs	X	X	X	X	
Hematology	X			X	
Biochemistry (including RBS, Serum prolactin (fasting), Serum lipase  )	X			X	
Pregnancy test 	X				
Test report for H. pylori 	X				
Upper GI Ultrasound	X				
Endoscopy 	X				
ECG	X				
Randomization		X			
Leeds Dyspepsia Questionnaire (LDQ)	X		X	X	
Short From Nepean Dyspepsia Index (SF-NDI) questionnaire		X		X	

NRS 11 onsite (baseline only)		X			
Patient diary distribution		X	X		
NRS 11 recorded in patient diary 		X	X		
Dispense Study drug		X	X		
Drug intake recorded in patient diary 		X	X		
Diary return			X	X	
Study drug return			X	X	
Study drug accountability and adherence assessment			X	X	
Adverse events	X	X	X	X	X
Concomitant medications	X	X	X	X	X
Treatment acceptance and ease of use assessment using Likert scale				X	

ET – End of treatment, ED – Early discontinuation, TC – Telephone contact, D – day, V – Visit

1. For women of child-bearing potential (including those without history of surgical sterilization and women with <2 years post-menopause)
2. H. pylori test report in medical history within 3 months before randomization, otherwise to be performed during screening.
3. Endoscopy in medical history within 6 months before randomization, otherwise to be performed during screening.
4. Symptoms will be recorded by the subject over the last 2 weeks prior to the next visit.
5. Will be calculated during analysis, not by investigator.
6. Will be recorded daily.
7. Serum Lipase at V1 (baseline) only.

